8.7 Assessments for safety

8.7.1 Adverse events

At all visits following screening investigator should ask subjects for any AEs. For more information on AEs refer to section [12](#).

8.7.2 Hypoglycaemic episodes

To avoid hypoglycaemic episodes subjects should be advised to avoid prolonged excessive fasting. Plasma glucose should always be measured and recorded when a hypoglycaemic episode is suspected.

All plasma glucose values:

- equal or below 3.9 mmol/L (70 mg/dL)
- or
- higher than 3.9 mmol/L (70 mg/dL) when they occur in conjunction with hypoglycaemic symptoms

should be recorded by the subjects in the diaries.

These must be transcribed into the CRF throughout the trial from Visit 2 to Visit 26.

The record should include the following information:

- The plasma glucose level before treating the episode (if available)
- Date of hypoglycaemic episode
- Time of hypoglycaemic episode
- Whether the episode was symptomatic
- Whether the subject was able to treat him/herself
- Time of antidiabetic treatment administration prior to episode
- Type of antidiabetic treatments taken within 24 hours prior to episode
- Time of last main meal prior to episode
- Whether the episode occurred in relation to exercise

The answer to the question: “Was subject able to treat him/herself?” should be answered “No” if oral carbohydrates, glucagon or IV glucose had to be administered to the subject by another person because of severe central nervous system (CNS) dysfunction associated with the hypoglycaemic episode. Oral carbohydrates should not be given if the subject is unconscious.

A hypoglycaemic episode form must be filled in for each hypoglycaemic episode. If the hypoglycaemic episode fulfils the criteria for an SAE and/or a medical event of special interest (MESI) then an adverse event (AE) form and a safety information form must also be filled in.

8.7.2.1 ADA classification of hypoglycaemia

According to the ADA the definition of a hypoglycaemic episode ([Figure 8–1](#)) is categorised as:

Severe hypoglycaemia: An episode requiring assistance of another person to actively administer carbohydrate, glucagon, or other resuscitative actions.

Asymptomatic hypoglycaemia: An episode not accompanied by typical symptoms of hypoglycaemia, but with a measured plasma glucose concentration ≤ 3.9 mmol/L (70 mg/dL).

Documented symptomatic hypoglycaemia: An episode during which typical symptoms of hypoglycaemia are accompanied by a measured plasma glucose concentration ≤ 3.9 mmol/L (70 mg/dL).

Relative hypoglycaemia: An episode during which the person with diabetes reports any of the typical symptoms of hypoglycaemia, and interprets those as indicative of hypoglycaemia, but with a measured plasma glucose concentration > 3.9 mmol/L (70 mg/dL).

Probable symptomatic hypoglycaemia: An episode during which symptoms of hypoglycaemia are not accompanied by a plasma glucose determination (but that was presumably caused by a plasma glucose concentration ≤ 3.9 mmol/L [70 mg/dL]).

[figure not shown]

Figure 8–1 ADA classification of hypoglycaemia

8.7.2.2 Additional definitions of hypoglycaemia

A hypoglycaemic episode will be defined as treatment emergent if the onset of the episode occurs after the first administration of IMP, and no later than one day after the last day on trial product (both inclusive).

Hypoglycaemic episodes will be defined as nocturnal if the time of onset is between 00:01 and 05.59 inclusive.

In normal physiology, symptoms of hypoglycaemia occur below a blood glucose level of approximately 2.8 mmol/L (50 mg/dL) or plasma glucose level 3.1 mmol/L (56 mg/dL). Therefore, Novo Nordisk has used this cut-off point to define confirmed hypoglycaemia.

A confirmed hypoglycaemic episode (referred to as minor hypoglycaemia) is defined as either:

- An episode with symptoms consistent with hypoglycaemia with confirmation by blood glucose < 2.8 mmol/L (50 mg/dL) or plasma glucose < 3.1 mmol/L (56 mg/dL), and which is handled by the subject him/herself,

or

- Any asymptomatic blood glucose value < 2.8 mmol/L (50 mg/dL) or plasma glucose value < 3.1 mmol/L (56 mg/dL).

8.7.3 Electrocardiogram – 12 lead

A 12-lead ECG must be performed at Visits 1, 17 and 25 and interpreted locally by the investigator in relation to the trial. Investigators evaluation must be documented, signed and dated on the ECG print out.

An ECG performed for any reason unrelated to this trial within 12 weeks prior to Visit 1 is acceptable provided no clinical symptoms suggestive of cardiac disease have occurred in the meantime. The investigator must still interpret, sign and date the ECG. If an ECG was performed before the informed consent and assent have been signed, it must be documented in the subject's medical record that the reason for performance was not related to this trial.

Only applicable to Israel: Child assent form is not applicable.

An ECG performed 2 weeks before Visits 17 and 25 is acceptable as Visits 17 and 25 data respectively.

8.7.4 Eye examination

A fundoscopy must be performed at Visits 1, 17 and 25 by the investigator or a local ophthalmologist according to local practice. Investigators evaluation must be documented in the subject's medical records.

If a fundoscopy has been performed within 12 weeks prior to Visit 1 and if the results are available, the procedure does not need to be repeated. The investigator must still interpret, sign and date the fundoscopy results. If a fundoscopy was performed before the informed consent and assent have been signed, it must be documented in the subject's medical record that the reason for performance was not related to this trial.

Only applicable to Israel: child assent form is not applicable.

A fundoscopy performed 2 weeks before Visits 17 and 25 is acceptable as Visits 17 and 25 data respectively.

8.7.5 Physical examination

At Visits 1, 7, 13, 17 and 25 a physical examination must be performed

Physical examination should include:

- Head, ears, eyes, nose, throat, neck
- Respiratory system

- Cardiovascular system
- Gastrointestinal system including mouth
- Musculoskeletal system
- Central and peripheral nervous system
- Skin
- General appearance
- Lymph node palpation
- Thyroid gland

Any abnormalities found at Visit 1 should be recorded as a concomitant illness. Any clinically significant worsening from Visit 1 as well as any new clinically significant findings during the trial must be reported as an AE (see section [12](#)).

8.7.6 Tanner staging

Pubertal status will be recorded in the CRF at Visits 7, 13, 17, 25, 27 and 28 for children-and adolescents. Pubertal development will be assessed by the Tanner staging in accordance with stages I-V³⁴. Assessment of testicular volume (by orchidometer) stages for boys will be included. The assessments must be conducted by personnel trained in pubertal assessments.

A Tanner staging assessment performed 2 weeks before Visits 7, 13, 17, 25, 27 and 28 is acceptable as Visits 7, 13, 17, 25, 27 and 28 data assessment respectively.

The Tanner staging assessment is no longer required to be performed, once the subject reaches the Tanner stage V, as judged by the investigator.

Evidence of accelerated pubertal development as judged by the investigator at Visit 1 should be recorded as concomitant illness. Acceleration of pubertal development after Visit 1 as judged by the investigator should be recorded as an AE

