17. At Visits 7, 13, 17, 25, 27 and 28 the assessments may be performed in the two weeks prior to the visits. Once the subject reaches the Tanner stage V, the Tanner staging assessment no longer requires to be performed.
18. A repeat bone age assessment will not be performed for subjects in whom the bone age assessment at the previous assessments indicates that the epiphyses are fused.
19. Visits 27 and 28 are only applicable for subjects treated with liraglutide for more than 3 months.
20. Prior to blood sampling for liraglutide antibodies subjects must attend without food or drink intake except for water and prescribed medication for at least 2 hours.
21. Visits 10A, 10B, 11A and 11B are only applicable to subjects treated with basal insulin.
22. Basal insulin titration only applicable at Visit 11.
23. Only applicable to subjects treated with basal insulin.
- Explanations:** Rand = randomisation; S = site visit; TC= telephone contact

3 Background information and rationale for the trial

In this document, the term investigator refers to the individual responsible for the overall conduct of the clinical trial at a trial site.

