8.7.7 Bone age assessment

An x-ray of left hand and wrist will be performed at Visits 7 and 25 for all subjects for evaluation of bone age. In addition subjects treated with liraglutide for more than three months will have an x-ray performed at Visits 27 and 28. A repeat bone age assessment will not be performed at subsequent visits (25, 27 or 28) for subjects for whom the bone age assessment at Visit 7, or at a later visit, indicates that the epiphyses are fused. The x-rays will be analysed by a central reader for determination of bone age. Further requirements and details will be described in the x-ray site manual.

An x-ray performed within 2 weeks prior to Visit 7, 25, 27 and 28 is acceptable.

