Data collected after treatment discontinuation or initiation of rescue treatment (see section [5.3.5](#)) will be considered missing in some of the efficacy analyses as described in section [17.3](#) and [17.4](#). Data collected after treatment discontinuation will be data from withdrawals collected at either Visit 17 or Visit 25 (see section [8.1.7](#)) in case the measurement is within the visit window (± 5 days) of a planned visit.

For safety variables missing values (including intermittent missing values) will be imputed using the last observation carried forward (LOCF) method on post-baseline measurements. All data for subjects receiving rescue treatment will be included.

Laboratory values below the lower limit of quantification (LLOQ) will be set to $\frac{1}{2}$ LLOQ.

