3.2 Handling of missing data

If an assessment has been made both at screening and randomisation, and if not otherwise specified, the value from the randomisation visit will be used as the baseline value. If the value measured at the randomisation visit is missing and the assessment also has been made at screening, then the screening value will be used as the baseline value.

For efficacy variables missing values will be imputed as described in protocol section 17.3 and 17.4 (section 3.5 and 3.6 in this SAP).

Data collected after treatment discontinuation or initiation of rescue treatment (see protocol section 5.3.5) will be considered missing in some of the efficacy analyses as described in protocol section 17.3 and 17.4 (section 3.5 and 3.6 in this SAP). Data collected after treatment discontinuation will be data from withdrawals collected at either Visit 17 or Visit 25 (see protocol section 8.1.7) in case the measurement is within the visit window (\pm 5 days) of a planned visit.

For safety variables missing values will not be imputed, except for 'pulse' which will be imputed as described for the secondary efficacy endpoints (section 3.6).

For subjects who received rescue medication, all data collected after initiation of rescue medication will be included.

Laboratory values below the lower limit of quantification (LLOQ) will be set to ½LLOQ.

Liraglutide
Trial ID: NN2211-3659
Statistical Analysis Plan

Date: 25 June 2018 Version: 2.0
Status: Final

Page:

13 of 25

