4.2 Handling of missing data

For safety variables it was stated in the protocol that missing values (including intermittent missing values) would be imputed using the last observation carried forward (LOCF) on post-baseline measurements. The analyses on safety parameters will be performed using a pattern mixture model with multiple imputation and missing values will therefore not be imputed using the LOCF method.

4.3 **Definition of fixed effects**

The fixed effect 'region' was not specified in the protocol, but in a sensitivity analysis the regions were described as: North America, Asia including Russia, Europe including Israel, South America including Mexico. To align with other NN2211 trials, the regions are defined as has been done overall for the NN2211 project. The only difference from the description in the protocol is that Russia is not assigned to region Asia, but is assigned to region Europe.

The fixed effect 'concomitant diabetes treatment at baseline' was described as 'diet and exercise alone vs. diet and exercise plus metformin and/or basal insulin'. As all subjects were to take metformin at baseline the definition is updated to with/without basal insulin at baseline (see section 3.3)

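### Tanner staging is waived after stage V and the SAP no longer carries it forward, so later Tanner summaries can understate pubertal progression and attenuate an arm difference

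*Protocol*

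**What the plan says.** **Schedule and waiver.** Protocol 8.7.6: "Pubertal status will be recorded in the CRF at Visits 7, 13, 17, 25, 27 and 28" (baseline, weeks 14, 26 and 52, and the one- and two-year follow-up). The same section then says: "The Tanner staging assessment is no longer required to be performed, once the subject reaches the Tanner stage V", as judged by the investigator. Flow-chart note 17 repeats the rule. Protocol 8.7.7 has a parallel rule for bone age: no repeat x-ray once the epiphyses are found fused.

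**Missing safety data, protocol section 17.** "For safety variables missing values (including intermittent missing values) will be imputed using the last observation carried forward (LOCF) method on post-baseline measurements".

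**Missing safety data, SAP.** Section 3.2: "For safety variables missing values will not be imputed", with pulse as the only exception. Section 4.2 explains that safety parameters are analysed by a pattern mixture model with multiple imputation, and concludes: "missing values will therefore not be imputed using the LOCF method".

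**Analysis.** Under SAP 3.6.3 safety endpoints are descriptive unless stated otherwise, and only pulse is given a model. Tanner progression is summarised as change from baseline at weeks 26 and 52. Under 3.6.4 it is summarised again at follow-up. SAP 2.2.3 stars it as an endpoint selected for public disclosure. Neither document gives a denominator for it or says how a waived assessment is counted.

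**The concern.** Stage V is the top of the scale, so a child who has reached it has a known status at every later visit. The protocol's LOCF, whatever its general weaknesses, gave the right answer here: a V first recorded at week 14 or 26 stayed V at week 52. With LOCF removed and nothing put in its place, a waived assessment becomes an empty cell. Whether the cell is empty depends on the outcome, because children leave the later summaries when they complete puberty. What remains is weighted towards slower progressors, and more strongly so in an arm that matures faster.

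The endpoint matters. Protocol section 18 (and 3.1.5, which applies to Sweden) assumes that risks in children match those in adults, with unforeseen effects on growth and pubertal development as the exception. Pubertal development at follow-up is also a stated secondary objective.

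**Working it through.** **Tracing the rule.** The plan gives no Tanner figure to reproduce, so the first check is which children can be absent on a literal reading.

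| Summary | Can be absent after progressing |
|---|---|
| Week 26 (Visit 17) | V first recorded at Visit 13 |
| Week 52 (Visit 25) | V first recorded at Visit 13 or 17 |
| Visits 27 and 28 | V first recorded at any earlier post-baseline visit |
| Bone age, Visits 27 and 28 | Fusion first seen at Visit 25 (for Visit 28, also at Visit 27) |

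Children already at V at baseline cannot progress. Their absence changes stage distributions and denominators but removes no acceleration signal.

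**Size: an illustration in which every input is assumed.** Each child below V advances one stage at a constant rate r per year. There are no withdrawals, and no staging is done after V. The rate is 0.5 (slow) or 1.0 (fast). Baseline shares at stages I to V are (5, 10, 25, 40, 20)%, (3, 7, 15, 35, 40)% or (2, 3, 10, 25, 60)%.

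Among children below V at baseline:
- True share progressed by time t (years): P = 1 − exp(−r·t).
- L = share who had already reached V at the previous staging visit and are now absent.
- Share progressed among those still observed: (P − L)/(1 − L).

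*Worked case: 20% at V at baseline, week 52.* Among those below V, the shares at IV, III, II and I are 0.5, 0.3125, 0.125 and 0.0625.
- Slow: P = 1 − exp(−0.5) = 0.393. L = 0.5×0.2212 + 0.3125×0.0265 + 0.125×0.0022 + a negligible stage I term = 0.119. Observed = (0.393 − 0.119)/(1 − 0.119) = 0.311.
- Fast: P = 1 − exp(−1) = 0.632 and L = 0.227. Observed = (0.632 − 0.227)/(1 − 0.227) = 0.524.
- Arm difference: true 0.632 − 0.393 = 0.239; observed 0.524 − 0.311 = 0.213. Loss = 0.026/0.239 = 11%.

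*All three baseline mixes:*

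| | Week 26 | Week 52 |
|---|---|---|
| Absent after progressing (L), slow | 6.6–8.1% | 11.9–14.5% |
| Absent after progressing (L), fast | 12.8–15.5% | 22.7–27.0% |
| Progressed, slow: true / observed | 22.1% / 15.3–16.7% | 39.3% / 29.1–31.1% |
| Progressed, fast: true / observed | 39.3% / 28.2–30.5% | 63.2% / 49.6–52.4% |
| Arm difference (points): true / observed | 17.2 / 12.9–13.8 | 23.9 / 20.6–21.3 |
| Share of difference lost | 20–25% | 11–14% |

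Week 52 progression is understated by 8 points (39.3 − 31.1) to 14 points (63.2 − 49.6).

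**Cross-check: all children at stage IV at baseline, constant half-year rates, V reached by week 26 absent at week 52.**
- 60% v 20% per half-year: true 1 − 0.4² = 84% v 1 − 0.8² = 36%, difference 48 points. Observed 60% v 20%, difference 40. Loss 8/48 = 17%.
- 50% v 20% per half-year: true 75% v 36%, difference 39 points. Observed 50% v 20%, difference 30. Loss 9/39 = 23%.

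Both week 52 losses exceed the 11–14% above but are of the same order, and both lie within 11–25%.

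**The case against.** **The exclusion is inferred.** An assessment that is no longer required may still be done, and a site may record V again. The SAP also does not say that a waived assessment counts as missing. This stands as a limit: the text permits the loss but does not make it certain. It is still what follows if the rules are applied as written.

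**Other measures carry the signal.** The visit at which V is first recorded stays in the data, and week 26 is summarised as well as week 52. Protocol 8.7.6 asks that acceleration after Visit 1, as judged by the investigator, be recorded as an AE. DHEAS, LH, FSH, estradiol and testosterone are summarised beside Tanner stage with no stage V stop. Week 52 bone age is read centrally for every subject not already fused at Visit 7. These safeguards are real but partial. AE reporting relies on judgement and is open-label after week 26, hormones and bone age do not measure Tanner stage, and no cumulative summary of stage V is specified.

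**Section 4.2 may mean only pulse.** Pulse is the one safety variable given a model, so the sentence can be read that way. Even so, it removes LOCF from all the others for a reason that does not apply to them.

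**A stronger inference to resist.** A reader might conclude that a real acceleration could be hidden altogether. One can build such a table. Take 20 children per arm at stage IV: 12 reach V by week 26 and 2 of the other 8 by week 52, against 4 and then 4 of 16. The truth is 14/20 = 70% v 8/20 = 40%, while week 52 shows 2/8 = 25% v 4/16 = 25%. But this needs the faster arm to slow from 60% to 25% per half-year while the other rises from 20% to 25%. Its own week 26 table would show 60% v 20% if V were first recorded at Visit 17. Nothing in the documents supports such rates.

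**Conclusion.** The point holds as understatement and attenuation, not concealment. Later Tanner summaries can leave out children because they progressed, which biases progression downward and shrinks an arm difference at weeks 26 and 52. Under constant advance rates, doubled in one arm, the loss is roughly 11–25% of the difference. That range rests on assumed baseline stages and rates, no withdrawals and no staging after V.

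Nor do the documents support reading this as a masked arm difference at follow-up. Visits 27 and 28, including bone age after fusion at Visit 25, apply only to subjects treated with liraglutide for more than 3 months. There is no comparator there, so the issue at those visits is understated progression alone.

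No confirmatory conclusion depends on this endpoint. It is worth correcting because it is selected for disclosure, addresses the risk singled out for this population, and is cheap to repair.

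**What to change.** - In SAP 3.2, 3.6.3 and 3.6.4, state that a recorded Tanner stage V, and fused epiphyses, is a known status that persists at all later scheduled visits where the assessment was waived. This uses recorded information and does not restore LOCF for other safety variables.
- Report progression and the cumulative proportion reaching stage V, by arm, among subjects below V at baseline, with denominators at each visit. At Visits 27 and 28 report the liraglutide subjects only.
- Reconcile SAP 4.2 with 3.2: the multiple-imputation rationale applies to pulse, and other safety variables need their own stated reason for dropping LOCF.

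The cost is a few sentences and a small programming change, with no new data. The one downside is that a stage V misjudged at an earlier visit is carried forward, as it would have been under the protocol's LOCF.

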8.7.7 Bone age assessment

An x-ray of left hand and wrist will be performed at Visits 7 and 25 for all subjects for evaluation of bone age. In addition subjects treated with liraglutide for more than three months will have an x-ray performed at Visits 27 and 28. A repeat bone age assessment will not be performed at subsequent visits (25, 27 or 28) for subjects for whom the bone age assessment at Visit 7, or at a later visit, indicates that the epiphyses are fused. The x-rays will be analysed by a central reader for determination of bone age. Further requirements and details will be described in the x-ray site manual.

An x-ray performed within 2 weeks prior to Visit 7, 25, 27 and 28 is acceptable.

8.7.8 Blood samples

Blood samples will be drawn at site at the specified time-points (section [2](#)) and analysed at the central laboratory to determine levels of the following safety parameters:

- Haematology
 - Haemoglobin
 - Haematocrit
 - Thrombocytes
 - Erythrocytes
 - Leucocytes
 - *Differential count:*
 - Eosinophils
 - Neutrophils
 - Basophils
 - Lymphocytes
 - Monocytes

- Biochemistry
 - creatinine
 - creatine kinase
 - urea
 - albumin
 - bilirubins (total)
 - ALAT
 - ASAT
 - Alkaline phosphatase
 - Sodium
 - Potassium
 - Calcium, total
 - Calcium, albumin corrected
 - Amylase
 - Lipase

- Hormones
 - Calcitonin (please refer to Appendix D for actions to be taken if calcitonin is > UNR)
 - Prolactin
 - FSH
 - Estradiol
 - LH
 - Testosterone

- DHEAS
 - CEA
 - TSH
 - IGF-1
 - IGFBP-3
- **Pregnancy test**
Females of childbearing potential will have a serum pregnancy test (beta-human chorionic gonadotropin) performed at Visits 1, 7, 13, 17 and 25. In addition they will have a urine pregnancy test performed at Visit 7 prior to randomisation. During the rest of the trial a urine-stick pregnancy test will be performed at the site if a menstrual period is missed. The investigator should comply with local laws with regard to pregnancy testing in minors during clinical trials.
Austria: A urine-stick pregnancy test will be performed at all visits to the clinic.

If a girl becomes of childbearing potential (has first menstrual period) during the trial a serum pregnancy test must be performed for that subject as soon as possible or at the latest at the next clinic visit.
- **Bone metabolism markers**
 - Alkaline phosphatase
 - P1NP
 - NTX
 - CTX
 - **Insulin antibodies:**
 - IA-2
 - anti-GAD
 - HIV
 - Hepatitis B and C

Liraglutide antibody samples

Blood samples for determination of anti-liraglutide antibodies will be drawn at Visits 7, 17 and 26. Unblinded subjects who are not treated with liraglutide should not have a blood sample drawn for determination of anti-liraglutide antibodies.

Samples will be analysed for anti-liraglutide antibody formation including cross reactivity to endogenous GLP-1. Samples from Visit 26 that are found to be positive for anti-liraglutide antibodies will be assessed for neutralising effect.

The blood samples collected for determination of anti-liraglutide antibodies will be stored until marketing authorisation for paediatric patient is given for liraglutide or as long as the local authorities permit the storage of blood samples, whichever comes first.

The antibody samples will be analysed at a special laboratory (please refer to Attachment I for details). The results of the antibody samples will only be reported to the investigator upon request at the end of trial.

